6.0 Registration Procedures

6.1 Registration Procedures

- 6.11 To register a patient, access the ACCRU web page at [REDACTED], go to the Application section and click on “Registration” and enter the registration/randomization application. The registration/randomization application is available 24 hours a day, 7 days a week. Back up and/or system support contact information is available on the Web site. If unable to access the Web site, call the Academic and Community Cancer Research United (ACCRU) Registration Office at [REDACTED] between the hours of 8 a.m. and 4:30 p.m. Central Time (Monday through Friday).

Instructions for the registration/randomization application are available on the above web page under the Study Resources section, “Application Training.”

Prior to initiation of protocol study intervention, this process must be completed in its entirety and an ACCRU subject ID number must be available as noted in the instructions. It is the responsibility of the individual and institution registering the patient to confirm the process has been successfully completed prior to release of the study agent. Patient registration via the registration/randomization application can be confirmed in any of the following ways:

- Contact the ACCRU Registration Office [REDACTED]. If the patient was fully registered, the ACCRU Registration Office staff can access the information from the centralized database and confirm the registration.
- Refer to “Application Training” at [REDACTED] click on “Registration, Installation & Entry Instructions”.

6.12 Correlative Research

A mandatory correlative research component is part of this study, the patient will be automatically registered onto this component (see Sections 3.19f, 14.1 and 17.11).

Cohort 1 only: An optional correlative research component is part of this study, there will be an option to select if the patient is to be registered onto this component (see Section 17.11).

- Patient has/has not given permission to give his/her tissue sample for optional correlative research testing planned as part of this study.

- 6.13 Documentation of IRB approval must be on file in the Registration Office before an investigator may register any patients. Approvals should be uploaded using the online ACCRU Regulatory Management System (ARMS).

In addition to submitting initial IRB approval documents, ongoing IRB approval documentation must be on file (no less than annually) with ACCRU. Approvals should be uploaded using the online ACCRU Regulatory Management System (ARMS). If the necessary documentation is not submitted in advance of attempting patient registration, the randomization will not be accepted and the patient may not be enrolled in the protocol until the situation is resolved.

Submission of annual IRB approvals is required until the study has been closed through your IRB.

6.14 Prior to accepting the registration/randomization, the registration/randomization application will verify the following:

- IRB approval at the registering institution
- Patient eligibility
- Existence of a signed consent form
- Existence of a signed authorization for use and disclosure of protected health information

6.15 At the time of registration, the following will be recorded:

- Patient has/has not given permission to store and use his/her tissue sample(s) for future research to learn about, prevent, or treat cancer.
- Patient has/has not given permission to store and use his/her tissue sample(s) for future research to learn, prevent, or treat other health problems (for example: diabetes, Alzheimer's disease, or heart disease).
- Patient has/has not given permission for ACCRU to give his/her tissue sample(s) to outside researchers.
- Patient has/has not given permission to store and use his/her blood sample(s) for future research to learn about, prevent, or treat cancer.
- Patient has/has not given permission to store and use his/her blood sample(s) for future research to learn, prevent, or treat other health problems (for example: diabetes, Alzheimer's disease, or heart disease).
- Patient has/has not given permission for ACCRU to give his/her blood sample(s) to outside researchers.

6.16 Treatment cannot begin prior to registration and must begin ≤ 10 days after registration.

6.17 Pretreatment tests/procedures (see Section 4.0) must be completed within the guidelines specified on the test schedule.

6.18 All required baseline symptoms (see Section 10.5) must be documented and graded.

6.19a Treatment on this protocol must commence at an ACCRU institution under the supervision of the treating physician who is either study site's principal investigator or co-investigator.

6.19b Study drug is available on site.

7.0 Protocol Treatment

7.1 Treatment Schedule

Arm	Agent	Dose Level	Route	Day
	Lenvatinib	20 mg	PO	Once daily Days 1 through 21 of each 21-day cycle
	Pembrolizumab	200 mg	IV	Day 1 of each 21-day cycle

7.11 Cohort 1: Lenvatinib-naïve patients will be administered both study drugs (pembrolizumab and lenvatinib) as of Cycle 1 Day 1. Each cycle is 21 days. The starting dose of oral lenvatinib is 20 mg (two 10-mg capsules).

7.12 Cohort 2: Pembrolizumab will be added to the treatment for patients who experience PD on lenvatinib alone. They will remain on or resume the dose of lenvatinib on which they experienced PD. Cycle 1 Day 1 will be the first day pembrolizumab is added to the treatment. Patients who have temporarily stopped lenvatinib dosing within 30 days of enrollment will restart lenvatinib at their prior dose along with pembrolizumab on Cycle 1 Day 1 of treatment. Patients entering Cohort 2 will have progressed on lenvatinib. These patients will remain on the dose they are taking at the time of study entry, which may have been previously reduced for side effect management, and will not exceed 20 mg by mouth daily.

- 7.2 Patients will be instructed on lenvatinib administration, to be taken with water orally once a day (with or without food) at approximately the same time each day, and granted treatment independence with nursing staff approval. If a patient misses a dose, and cannot be taken within 12 hours, then that dose should be omitted and the next dose should be taken at the usual time of administration. If a patient vomits after taking the daily dose of lenvatinib, DO NOT repeat dosing. Resume regular dosing the next day. NOTE: The patient will be requested to maintain a medication diary to document time and date when each dose of lenvatinib is taken. Patient will also document number of pills/dose of medication taken, and note any vomiting subsequent to dosing. The medication diary will be returned to clinic staff at each examination visit (see Section 4.0).
- 7.3 Pembrolizumab, 200 mg, will be administered as a 30-minute IV infusion every 21 days (treatment cycle intervals may be increased based on toxicities as described in section 8.3). Sites should target infusion timing to be as close to 30 minutes as possible, however, given the variability of infusion pumps from site to site, a window of -5 and +10 minutes is permitted (i.e., infusions lasting between 25 minutes to 40 minutes are acceptable).
- 7.4 Study treatment with pembrolizumab may be administered up to 3 days before or after the scheduled Day 1 of each cycle due to administrative reasons.
- 7.5 For this protocol, the patient must return to the consenting ACCRU institution for evaluation day 1 of cycles 2, 3, 5, 7, 9, 11, 13, 15, 17 and 19 (see Section 4.0 Test

Schedule, Active Monitoring Phase).

- 7.6 Treatment with study-specific drugs by a local medical doctor (LMD) is not allowed.
- 7.7 Patients who develop PD in the CNS only may receive radiotherapy and continue treatment on study after completion of radiotherapy. Patient must be clinically stable and have been off systemic corticosteroids for at least 14 days at the time of recommencement of treatment. **NOTE: Both lenvatinib and pembrolizumab should be withheld for a minimum of 3 days prior to radiation and for 3 weeks after radiation.**
- 7.8 Accumulating evidence indicates a minority of patients treated with immunotherapy may derive clinical benefit despite initial evidence of PD. Patients receiving treatment in this study will be permitted to continue treatment beyond initial PD, if the initial PD happens in the first 12 weeks post-registration (by RECIST 1.1), as long as they meet the following criteria:
- Investigator-assessed clinical benefit (e.g. absence of rapid disease progression and absence of progressive tumor at a critical anatomic site that requires urgent alternative intervention), and
 - The patient is tolerating study drug.
 - Patient does not continue to progress at 4 week follow-up imaging after PD first noted.

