A fixed dose regimen will simplify the dosing regimen to be more convenient for physicians and to reduce potential for dosing errors. A fixed dosing scheme will also reduce complexity in the logistical chain at treatment facilities and reduce wastage.

The starting dose of lenvatinib 24 mg by mouth daily is the FDA-approved dose for radioiodine-refractory progressive differentiated thyroid carcinoma based upon the dosing used in the phase III SELECT trial that established the efficacy of lenvatinib in this setting. An ongoing phase Ib basket trial of lenvatinib plus pembrolizumab in solid tumors (thyroid was not included), showed good tolerability of the combination and recommends a starting dose of 20 mg daily lenvatinib in combination with 200 mg iv pembrolizumab every 3 weeks, which will be the starting doses in Cohort 1 (personal communication). Patients entering Cohort 2 will have progressed on lenvatinib. These patients will remain on the dose they are taking at the time of study entry, which may have been previously reduced for side effect management, and will not exceed 20 mg by mouth daily.

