2.0 Goals

2.1 Primary

- 2.11 To investigate the clinical efficacy, as indicated by the rate of complete response (CR) per RECIST 1.1, of combination therapy with pembrolizumab and lenvatinib in lenvatinib-naïve patients with progressive radioiodine-refractory DTC (Cohort 1).
- 2.12 To determine the overall response rate (ORR) by the addition of pembrolizumab to patients with radioiodine-refractory DTC who have progressive disease on lenvatinib alone (Cohort 2).

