3.1 Inclusion Criteria

- 3.11 Age \geq 18 years.
- 3.12 Locally recurrent and unresectable and/or distant metastatic differentiated thyroid cancer (DTC), histologically or cytologically confirmed. The diagnosis of DTC includes the following subtypes: Papillary thyroid cancer (PTC) (including but not limited to variants such as follicular variant, tall cell, columnar cell, Hürthle cell variant of papillary carcinoma, and poorly differentiated), Follicular thyroid cancer (FTC), including Insular variant, Hürthle cell carcinoma and poorly differentiated thyroid cancer.
- 3.13 Measurable disease meeting the following criteria (see Section 11.0):
 - 3.13a At least 1 lesion of \geq 1.0 cm in the longest diameter for a non-lymph node or \geq 1.5 cm in the short-axis diameter for a lymph node which is

serially measurable according to RECIST 1.1 using computerized tomography/magnetic resonance imaging (CT/MRI). If there is only one target lesion and it is a non-lymph node, it should have a longest diameter of ≥ 1.5 cm.

- 3.13b. Lesions that have had external beam radiotherapy (EBRT) or loco-regional therapies such as radiofrequency (RF) ablation must show evidence of progressive disease based on RECIST 1.1 to be deemed a target lesion.
- 3.14 For Cohort 1 Only: Evidence of disease progression ≤ 14 months prior to registration according to RECIST 1.1, as confirmed by the site study PI.
- 3.15 For Cohort 2 Only: Progressive disease (PD) on lenvatinib per RECIST 1.1 ≤ 60 days prior to registration, as confirmed by the site study PI. Patients need to have documented imaging and measurement of RECIST target lesions within 30 days of starting pembrolizumab.
- 3.16 Radioiodine (RAI)-resistant disease as defined by one or more of the following criteria:
- a. One or more measurable lesions that do not demonstrate RAI uptake
 - b. One or more measurable lesions progressive by RECIST 1.1 ≤ 14 months of prior RAI therapy.
 - c. One or more measurable lesions present after cumulative RAI dose of ≥ 600 mCi.
 - d. One or more measurable lesions that are FDG-avid (>5 SUV), if PET/CT scan performed. These lesions may also be RAI-avid.
- 3.17 ECOG Performance Status (PS) 0 or 1. (Form is available on the ACCRU web site)

- 3.18 The following laboratory values obtained ≤ 30 days prior to registration, unless otherwise specified:

System	Laboratory Value
Hematological	
Absolute neutrophil count (ANC)	$\geq 1,500$ /mcL
Platelets	$\geq 100,000$ / mcL

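### Section 7.12 gives Cohort 2 more than one reference dose of lenvatinib and no order of precedence, so the same patient can be dosed differently and lenvatinib can change as pembrolizumab starts

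*Combined protocol and SAP*

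**What the plan says.** Section 7.12 contains four statements about lenvatinib in Cohort 2.

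- Dose at progression: "They will remain on or resume the dose of lenvatinib on which they experienced PD".
- Interrupted patients: those who stopped temporarily within 30 days of enrolment "will restart lenvatinib at their prior dose along with pembrolizumab on Cycle 1 Day 1 of treatment". The prior dose is not defined.
- Dose at entry: "These patients will remain on the dose they are taking at the time of study entry, which may have been previously reduced".
- Ceiling, completing that same sentence: "for side effect management, and will not exceed 20 mg by mouth daily".

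Section 1.8 repeats the entry-dose and ceiling wording but not the progression-dose sentence. It also states: "The starting dose of lenvatinib 24 mg by mouth daily is the FDA-approved dose for radioiodine-refractory progressive differentiated thyroid carcinoma". Inclusion criterion 3.15 requires "Progressive disease (PD) on lenvatinib per RECIST 1.1 ≤ 60 days prior to registration, as confirmed by the site study PI", with target lesions imaged within 30 days of starting pembrolizumab. Section 6.16 allows up to 10 days from registration to treatment. Footnote a of the dose-level table in 8.1 rules out raising a dose once it has been reduced.

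The Cohort 2 objective in 2.12 is "To determine the overall response rate (ORR) by the addition of pembrolizumab to patients with radioiodine-refractory DTC who have progressive disease on lenvatinib alone".

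**The concern.** The paragraph does not say which statement prevails when they differ. Two sites could each follow a sentence of 7.12 and give the same patient different doses. That makes it a contradictory treatment rule, which is more than a missing detail.

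It bears on interpretation because Cohort 2 has one arm, judged against an assumed 5% response rate (16.14), and its objective is worded as the response rate from adding pembrolizumab. A response is easiest to read that way if lenvatinib was unchanged when pembrolizumab began. Where lenvatinib is changed or restarted at about the same time, the reader needs to know. As written, the plan neither prevents this nor has a listing that would show it.

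**Working it through.** **The plan's own figures.** Cohort 2 enrols 15 patients, continues if at least 1 responds, and is positive if at least 4 of 25 respond (16.151, 16.152). The exact probability of a positive result at true rate p is the sum over x = 1 to 15 of P(X1 = x | 15, p) × P(X2 ≥ 4 − x | 10, p).

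- At p = 0.25: 0.9008. The stated 90% power reproduces.
- At p = 0.05: 0.0336, under the stated 0.05, which fits a nominal ceiling.

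Nothing in this point changes these numbers. The problem lies in the treatment text.

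**Timing.** Progression may be 60 days before registration, and treatment may start 10 days after it. So 60 + 10 = 70 days can separate progression from Cycle 1 Day 1. No criterion requires an unchanged dose over that period. Criterion 3.22 excludes only patients who stopped lenvatinib for toxicity, and 3.29u only limits the number of earlier inhibitors. Neither excludes a patient taking more than 20 mg.

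**The sentences side by side.** Write P for the dose at progression and E for the dose at entry.

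| Patient | Progression-dose sentence | Entry-dose sentence | Ceiling | Consistent? |
|---|---|---|---|---|
| P = E, at most 20 mg, no interruption | P | P | met | Yes |
| P = E = 24 mg | 24 mg | 24 mg | at most 20 mg | No: the ceiling contradicts both |
| P = 24 mg, E at most 20 mg | 24 mg | E | met by E only | No |
| P and E differ, both at most 20 mg | P | E | met by both | No |
| On hold at entry | resume P | no dose is being taken | applies | Depends on what prior dose means |

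In the second row, if the ceiling governs, the reduction is at least (24 − 20)/24 = 4/24 = 16.7%, and it coincides with the first pembrolizumab infusion. In the third row the change has already happened before entry.

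In the last row the prior dose could be P or the last dose before the hold. These differ if the dose was altered after progression. Even when they are the same, lenvatinib restarts on the same day as pembrolizumab.

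**Footnote a of 8.1.** If it covers reductions made before entry, a patient reduced after progression cannot go back to P, although the progression-dose sentence allows resuming it. If it covers only reductions on study, there is no clash. The text does not say which.

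**Other places.** The treatment table in 7.1, dose level 0 in 8.1 and the patient diary all show 20 mg only. They do not address a Cohort 2 patient entering on another dose.

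**The case against.** The strongest reply is that a general rule followed by an explicit limit is ordinarily read as that dose up to the limit. No section permits 24 mg on study, and 1.8 carries only the entry-dose and ceiling wording. This is a fair reading of the 24 mg case, and it stands as far as it goes. But 7.12 does not state it, it still means that lenvatinib changes as pembrolizumab starts for a patient who enters on 24 mg, and it does not settle a dose changed between progression and entry.

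A second reply is that 16.151 asks only whether the combination merits further testing. Section 16 contains no estimate of pembrolizumab's separate contribution, and a single-arm comparison with an assumed rate limits attribution whatever the dose wording. That also stands. The dose conflict adds to a limit the design already has; it does not create it. Likewise, 2.12 speaks of progression on lenvatinib alone and does not promise an unchanged dose.

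A reader might infer that the conflict inflates the chance of a false positive in Cohort 2. The documents do not support that. The only dose changes they describe before entry are reductions for side effects, and a lower lenvatinib dose would not obviously raise the response rate. Restarting lenvatinib after a hold could contribute to a response, but no rate is given. The direction is open.

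**Conclusion.** The contradiction is real and sits in the current text. It affects patients whose lenvatinib dose changed between progression and entry, patients who progressed on 24 mg, and possibly interrupted patients. For an uninterrupted patient on one dose of 20 mg or less throughout, the sentences agree.

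The only size the documents allow is per patient: a reduction of at least 16.7% for someone who enters on 24 mg, assuming the ceiling prevails. The number affected is not given and could be anywhere from 0 to 25 of the evaluable patients. That 24 mg is foreseeable rests on 1.8 naming it as the approved starting dose.

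A reader might also infer that patients with equal doses at progression and at Cycle 1 Day 1 show the effect of pembrolizumab alone. They do not necessarily: an interrupted patient can have equal doses and still restart lenvatinib together with pembrolizumab. The point therefore supports clearer text and transparent reporting. It does not support a changed decision rule or a claim of attribution in a subgroup.

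**What to change.** 1. The sponsor should reconcile the sentences of 7.12 with each other, with 1.8 and with footnote a of 8.1, so that one reference dose and one order of precedence apply. The text should cover a patient who progressed above the ceiling, a patient whose dose changed after progression, and the meaning of prior dose for an interrupted patient. This review takes no view on which dose is right.

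2. Record, if not already collected, the lenvatinib dose at progression, the dose at Cycle 1 Day 1 and any interruption between them. Section 18.1 lists a Cohort 2 form for prior VEGFR-targeted therapy that could hold these items. Its fields are not shown, so some may be there already.

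3. List confirmed responses descriptively in three groups: lenvatinib unchanged and uninterrupted, changed, or interrupted and restarted. Readers can then see how many responses coincide with a lenvatinib change. Make no attribution claim from these groups.

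Leave the 4-of-25 rule and the sample size as they are. The cost is a wording amendment, at most a few form fields and one descriptive table. The groups will be small, since at most 25 patients are evaluable.

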8.0 Dosage Modification Based on Adverse Events

Strictly follow the modifications in this table for the first **two** cycles, until individual treatment tolerance can be ascertained. Thereafter, these modifications should be regarded as guidelines to address side effects. If multiple adverse events are seen, administer dose based on greatest reduction required for any single adverse event observed. Reductions or increases apply to treatment given in the preceding cycle and are based on adverse events observed since the prior dose.

ALERT: *ADR reporting may be required for some adverse events (See Section 10)*

8.1 Dose Levels (Based on Adverse Events in Tables 8.2 and 8.3)

Dose Level	Lenvatinib ^a	Pembrolizumab
0 ^b	20 mg orally once a day	200 mg IV every 21 days
-1	14 mg orally once a day	No dose reduction allowed
-2	10 mg orally once a day	No dose reduction allowed
-3	4 mg orally once a day	No dose reduction allowed

^a Once the dose has been reduced, it should not be increased at a later date.

^b Dose level 0 refers to the starting dose.

8.2 Dose Modifications for **Lenvatinib**-Related Toxicities

Treatment-Related Toxicity^{a, b} including hepatic injury and venous thromboembolic events	Management	Dose Modification
Grade 1 and Tolerable Grade 2		
	Continue Treatment	No change
Intolerable Grade 2^c or Grade 3^{d, e}		
First occurrence	Hold until resolved to Grade 0-1 or baseline ^f	14 mg orally once a day
Second occurrence (same toxicity or new toxicity)	Hold until resolved to Grade 0-1 or baseline ^f	10 mg orally once a day
Third occurrence (same toxicity or new toxicity)	Hold until resolved to Grade 0-1 or baseline ^f	4 mg orally once a day
Fourth occurrence (same toxicity or new toxicity)	Hold until resolved to Grade 0-1 or baseline ^f	Contact ACCRU Quality Assurance Specialist
Grade 4^g: Discontinue Study Treatment		

NOTE: See CTCAE v4 for grading:

Collect all CTC grades of AEs, decreasing and increasing grade.

- a. A delay of study treatment for more than 28 days (due to treatment-related toxicities) will require a discussion with the ACCRU Quality Assurance Specialist before treatment can be resumed (see protocol resource page).
- b. Initiate optimal medical management for nausea, vomiting, and/or diarrhea prior to any study treatment, interruption, or dose reduction.
- c. Grade 2 toxicities will be determined to be tolerable or intolerable by both the subject and investigator. If Grade 2 toxicity is determined to be intolerable, the dose of study drug will be reduced with or without dose interruption. Interruption for Grade 3 toxicities is mandatory.
- d. Weight loss of any grade may not require dose reduction, but should be managed based on the judgment of the investigator. Subjects with weight loss requiring dose interruption and reduction do not need to return to baseline weight to restart lenvatinib. Based on the judgment of the investigator, subjects may be restarted at a lower dose of lenvatinib for weight loss. Consultation with a registered dietician may be helpful in managing weight loss.
- e. Not applicable to abnormal clinical laboratory values that are not clinically relevant based on the judgment of the investigator (e.g., ALT, AST, γ -GTP values $< 10 \times$ ULN, and Na).
- f. For hematology toxicities, restart treatment after toxicity resolves to Grade ≤ 2 .
- g. Excluding laboratory abnormalities judged to be non-life-threatening, in which case manage as Grade 3.

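### Table 8.2 prints lenvatinib doses that fit only a start above 14 mg, although Cohort 2 patients may enter lower; separately, the diary tells every patient to take 20 mg.

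*Combined protocol and SAP*

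**What the plan says.** Cohort 1 starts lenvatinib at 20 mg. Under section 7.12, Cohort 2 patients stay on the dose they take at entry, "which may have been previously reduced for side effect management, and will not exceed 20 mg by mouth daily".

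For an intolerable grade 2 or a grade 3 toxicity, Table 8.2 assigns a dose to each occurrence: first, "14 mg orally once a day"; second, 10 mg; third, 4 mg; fourth, contact the ACCRU Quality Assurance Specialist. The rows carry no qualifier for cohort or entry dose. Footnote c says that for intolerable grade 2 "the dose of study drug will be reduced with or without dose interruption", and it makes the interruption mandatory for grade 3.

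Three other places bear on how the table is read:

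- Section 8.0 makes the table strict for two cycles and adds: "Thereafter, these modifications should be regarded as guidelines to address side effects". The same paragraph says "Reductions or increases apply to treatment given in the preceding cycle".
- Section 8.1 gives the ladder 20, 14, 10, 4 mg. Footnote a: "Once the dose has been reduced, it should not be increased at a later date". Footnote b: "Dose level 0 refers to the starting dose"; the table sets that level at 20 mg.
- Section 8.21, for hypertension only, spells out the step from 20 to 14, 14 to 10 and 10 to 4 mg.

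Sections 8.23 (liver injury), 8.24 (venous thromboembolism) and 8.25 (PRES) refer to Table 8.2. Section 8.22 (proteinuria) refers to a Table 2, apparently the same table.

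Item 1 of the lenvatinib diary instructs the patient to take two 10 mg capsules daily, 20 mg in total. Only one version of the diary is given.

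**The concern.** The rows of Table 8.2 work as reductions only if the patient starts above 14 mg, and section 7.12 expects some patients to start lower. For them the printed dose can equal or exceed the dose on which the toxicity occurred. This is a rule that gives the wrong dose, not a missing detail.

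At stake are patient safety and consistent dosing. A site that follows the row may restart a patient with no reduction after a grade 3 event. A site that reasons from sections 8.0 and 8.21 will step down. The same case is then handled differently at different sites, in the cycles where the protocol asks for strict adherence.

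The diary raises a separate problem: a patient in either cohort on a reduced dose holds a document that prints 20 mg.

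**Working it through.** There is no stated figure to reproduce and no error rate or sample size is involved. The check compares each printed row with the dose being taken.

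**Inputs.** Ladder 20, 14, 10, 4 mg (8.1). Printed doses 14, 10, 4 mg for occurrences 1 to 3 (8.2). Entry dose anywhere up to 20 mg in Cohort 2 (7.12). No increase after a reduction (8.1 footnote a). Cycle length 21 days (7.1). Strict period two cycles (8.0).

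**Assumption.** Occurrences are counted on study, from zero. The protocol does not say so explicitly.

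**Printed rows, with any increase barred.** Each change is the new dose minus the dose being taken.

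| Entry dose | Occurrence 1 (prints 14) | Occurrence 2 (prints 10) | Occurrence 3 (prints 4) | Rows with no reduction |
|---|---|---|---|---|
| 20 mg | 14 (−6) | 10 (−4) | 4 (−6) | 0 of 3 |
| 14 mg | 14 (0) | 10 (−4) | 4 (−6) | 1 of 3 |
| 10 mg | stays at 10 (0) | 10 (0) | 4 (−6) | 2 of 3 |
| 4 mg | stays at 4 (0) | stays at 4 (0) | 4 (0) | 3 of 3 |

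**One level below the current dose, as in 8.21.**

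| Entry dose | Occurrence 1 | Occurrence 2 | Occurrence 3 |
|---|---|---|---|
| 20 mg | 14 | 10 | 4 |
| 14 mg | 10 | 4 | contact specialist |
| 10 mg | 4 | contact specialist | – |
| 4 mg | contact specialist | – | – |

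**Gap at the first occurrence.** 14 mg entrant: 14 − 10 = 4 mg per day. 10 mg entrant: 10 − 4 = 6 mg per day. For a 4 mg entrant there is no lower rung, so the difference is a call to the specialist, not milligrams. Entrants above 14 mg get a reduction from every row.

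**By grade.** For grade 3, footnote c mandates the interruption but is silent on the restart dose, so the row alone sets it. For intolerable grade 2, footnote c requires a reduction, so a row that gives none contradicts its own footnote, and nothing in the table says how large the step should be.

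**Strict window.** 2 × 21 = 42 days.

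**Diary.** Item 1 exceeds a 14 mg dose by 20 − 14 = 6 mg per day and a 10 mg dose by 20 − 10 = 10 mg per day.

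**The case against.** The best defence is that the protocol, read as a whole, already points to a step down. Section 8.0 ties reductions to the preceding cycle, 8.1 supplies the ladder, and 8.21 shows the step from each dose. That stands as evidence of intent. It does not repair the rows: 8.0 gives a reference point but no step size, and the steps in 8.21 cover hypertension only.

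A second defence is that toxicities before entry might count as occurrences. A patient reduced once, to 14 mg, would then be on the second row (10 mg), and one reduced twice, to 10 mg, on the third (4 mg). Both match one level down. The protocol does not state this reading, and it is unstable. Section 1.8 gives the approved start as 24 mg, so a patient who came down through 20 to 14 mg would have two earlier reductions and would land on the third row, 4 mg.

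Other safeguards narrow the point. "A delay of study treatment for more than 28 days" for toxicity needs a discussion before restart. Footnotes d and e leave weight loss and laboratory values without clinical relevance to judgment, and d allows a lower restart dose. Section 8.25 says only that adjustments may be needed. Grade 4 stops treatment, and 3.22 excludes patients who discontinued lenvatinib for toxicity.

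For the diary, section 7.2 provides for instruction, nursing approval and return of the diary. Item 3 refers to the prescribed dose, and staff have a field for the planned dose. These lower the risk but leave item 1 wrong.

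Two stronger readings are tempting. A reader might infer that the table orders an increase to 14 mg for a 10 or 4 mg entrant. Footnote a of 8.1 bars that, and footnote c of 8.2 rules it out for grade 2. A reader might also infer that a patient with intolerable grade 2 toxicity may restart unreduced. Footnote c says otherwise; only the size of the step is missing.

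**Conclusion.** Wrong as written, and worth correcting. For Cohort 2 patients entering at 14, 10 or 4 mg, the printed rows give no reduction at one, two or three of the three occurrences after a grade 3 lenvatinib-related toxicity other than hypertension. At the first occurrence the restart is 4 mg per day (14 mg entrant) or 6 mg per day (10 mg entrant) above the evident intent. For intolerable grade 2, the reduction is required but its size is undefined and the rows conflict with it.

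These figures rest on counting on-study occurrences from zero and on reading 8.1 footnote a as covering reductions made before entry. The exposure lies mainly in the first 42 days, after which the table is a guideline.

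The documents do not say how many Cohort 2 patients will enter at 14 mg or below, so no count of affected patients can be given. Nor do they support a claim that guidance is wholly absent, or that the sample size or error rates are affected.

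The diary error is separate and applies to any patient on a reduced dose in either cohort.

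**What to change.** 1. **Table 8.2, first to third occurrence.** Replace the fixed doses with: *Restart one dose level below the dose being taken (20 to 14, 14 to 10, 10 to 4 mg; from a dose between levels, the next lower level). If already at 4 mg or below, contact the ACCRU Quality Assurance Specialist.* The sequence for a 20 mg start is unchanged.
2. **Section 8.1, footnote b.** Replace with: *Level 0 is the Cohort 1 starting dose. Cohort 2 patients enter at their current dose, and any reduction is to the next lower dose in this table.* This also covers entry doses between levels.
3. **Diary item 1.** Replace the fixed 20 mg with a line, completed by staff, for the capsules and total daily dose, and reissue the diary after any dose change.
4. **Section 8.22.** Correct the reference from Table 2 to Table 8.2.

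The cost is a few lines of wording in sections 8.1, 8.2 and 8.22 and one diary line. No dose level is added, and the sample size and analysis do not change.
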